#### **9.2.7. Events of Clinical Interest**

ECIs will include CTCAE Grade  $\geq 3$  diarrhea, CTCAE Grade  $\geq 3$  abdominal pain, CTCAE Grade  $\geq 3$  transaminase increases, and fat-soluble vitamin deficiency; these will be subject to specialized, targeted data collections. Please refer to [Appendix 3](#) for algorithms to assess transaminase increases and/or potential DILI events.

Additional ECIs may be identified during the course of the study.

Specifics regarding events to be designated as ECIs, along with reporting instructions/timelines, will be included in the eCRF completion guidelines. ECIs that meet seriousness criteria shall be subject to expedited reporting as outlined in [Sections 9.2.1](#) and [9.2.5](#).

#### **9.2.8. Overdose and Special Reporting Situations**

Overdose is defined as intentional or unintentional intake of a dose of investigational product higher than the protocol-prescribed dose. Treatment of overdose with volixibat would be consistent of general supportive measures, if applicable, including hydration and monitoring for fat-soluble vitamin deficiencies. In the event of an overdose, the investigator should contact the medical monitor within 24 hours of site personnel awareness of the event. The investigator must closely monitor the participant for any AE/SAEs and laboratory abnormalities for at least 24 hours.

Decisions regarding dose interruptions or modifications will be made by the investigator in consultation with the medical monitor based on the clinical evaluation of the participant. The sponsor does not recommend specific treatment for an overdose.

Abuse, misuse, overdose, or medication errors are not considered AEs on their own; however, they must be reported to the sponsor whether or not they result in an AE/SAE as described in [Section 9.2.1](#). All AEs associated with abuse, misuse, overdose, or medication errors should be reported as per the standard process for reporting any AE. The 24-hour reporting requirement for SAEs does not apply to reports of abuse, misuse, overdose, or medication errors unless these result in an SAE.

The categories below are not mutually exclusive; the event can meet >1 category.

- Abuse: Persistent or sporadic intentional intake of investigational product when used for a nonmedical purpose (e.g., to alter one's state of consciousness or get high) in a manner that may be detrimental to the individual and/or society
- Misuse: Intentional use of investigational product other than as directed or indicated at any dose (Note: This includes a situation where the investigational product is not used as directed at the dose prescribed by the protocol)
- Overdose: Intentional or unintentional intake of a dose of investigational product higher than the protocol-prescribed dose
- Medication Error: An error made in prescribing, dispensing, administration, and/or use of an investigational product. For studies, medication errors are reportable to the sponsor only as defined below.
  - Cases of participants missing doses of the investigational product are not considered reportable as medication errors.
  - Medication errors should be collected/reported for all products under investigation. The administration and/or use of the unassigned treatment is/are always reportable as a medication error.
  - The administration and/or use of an expired investigational product should be considered as a reportable medication error.

#### **9.2.8.1. Disease Progression**

Disease progression itself (i.e., worsening of ICP) is not considered an AE unless it is considered atypical in presentation and/or considered to be related to the study drug. Signs or symptoms of disease progression do not need to be reported as AEs/SAEs unless there is uncertainty as to their cause, in which case they may be reported as AEs.

#### **9.2.8.2. Liver Safety Monitoring**

Please refer to [Appendix 3](#) for algorithms to assess liver safety and potential DILI events.

### **9.2.9. Lactation/Exposure during Breastfeeding**

Mothers who are breastfeeding at screening or planning to breastfeed at any time starting with the screening visit through completion of study drug with volixibat are excluded from study participation.

The potential for volixibat to be excreted in human milk has not been studied at this time. However, given that volixibat is minimally absorbed and only sporadically detectable in plasma (most concentrations below the LLOQ), after single doses up to 300 mg and multiple doses up to 80 mg BID with no observed accumulation, identification of detectable volixibat concentrations in human milk would be unlikely at the doses intended for study.

The protocol-specified treatment period for volixibat ends with delivery. There are no contraindications to initiation of breastfeeding the neonate immediately upon delivery.

### **9.2.10. Follow-Up**

After the initial AE/SAE/AESI/ECI report, the investigator is required to proactively follow each participant at subsequent visits/contacts. All events will be followed until the event resolves, returns to baseline, stabilizes, is otherwise explained, no further improvement is anticipated based on the medical judgement of the treating physician, or the participant is lost to follow-up.

Investigators are not obligated to actively seek AEs or SAEs after study participants exit the study. However, if the investigator learns of any SAEs that occurred in a participant after study exit and he or she considers the event to be reasonably related to the study drug, the investigator must notify the sponsor within 24 hours after awareness.

## **10. STATISTICAL CONSIDERATIONS**

All predefined statistical analyses for the final analysis will be performed after the database is locked. All statistical analyses will be performed using SAS software (SAS Institute, Cary, NC, USA) version 9.4 or higher.

The statistical analysis plan (SAP) will provide the comprehensive statistical methods and definitions for the analysis of the efficacy and safety data, as well as describe the approaches to be taken for summarizing other study information, such as participant disposition, demographic and baseline characteristics, medical and disease history, study medication exposure, and prior medications. All study data will be presented in participant listings.

The study has 2 separate, self-standing parts, and each will have its own separate analyses. Of note, a pooled safety analysis combining Parts 1 and 2 may be considered, whereas Part 1 will not be combined in any of the efficacy analyses. Additionally, efficacy analyses within Part 1 will be summarized separately based on UDCA usage at baseline.

All inferential statistical tests will be 2-sided. Summary statistics for continuous variables will include mean, median, standard deviation, SEM, minimum, maximum, and quartiles. Summary of categorical variables will include sample size, number of occurrences, and percentages (95% CIs will be provided where appropriate).

The SAP will be finalized prior to unblinding to preserve the integrity of the statistical analysis and study conclusions.

## 10.1. Sample Size Determination

Part 1 of the study is designed for estimation without formal statistical testing; hence, there are no formal power considerations. For example, with 20 participants per group and assuming a standard deviation of 25 for each group, a 95% CI for the mean for each volixibat arm would have a half width of 11.

For the power calculations for Part 2, it is assumed that only a single dose will be selected at the end of Part 1, and a 2-sided alpha 0.05 will be used to test whether there is a difference between the 2 groups. Thus, for Part 2, a sample size of 100 participants per arm has 80% power to detect mean difference of 10 with standard deviation of 25. Power was calculated using SAS, version 9.4.

## 10.2. Population for Analyses

For purposes of analysis, the populations are defined in [Table 3](#).

**Table 3** Analyses Populations

Population	Description
Enrolled	All participants who sign the ICF
ITT	All randomized participants
mITT	All randomized participants who receive at least 1 dose of study drug (partial or complete). Participants will be analyzed according to the treatment to which they were randomized.
PP	All participants in the mITT population who do not experience any major protocol violations
Safety	All participants who receive at least 1 dose of study drug. Participants will be classified based upon the treatment they actually receive.

ICF=informed consent form; ITT=intent-to-treat; mITT=modified intent-to-treat;  
PP=per-protocol.

## 10.3. Participant Disposition, Demographics, and Baseline Characteristics

Participant disposition, demographic and baseline characteristics, disease history, prior medications, treatment exposure, and compliance will be summarized by treatment group. Study completion status and reasons for discontinuation will also be displayed. The safety population will be used for these summaries. Medical and surgical history and protocol violations/deviations will be presented in participant listings.

## 10.4. Statistical Analyses

Data from Part 1 will be included in the overall safety/tolerability summaries; however, participants in Part 1 will not be combined with those from Part 2 for the statistical inference performed in Part 2. Sampling to assess plasma exposures to volixibat may be discontinued in Part 2 pending results in Part 1.

## 10.4.1. Efficacy Analyses

### 10.4.1.1. Primary Efficacy Endpoint

For Part 2, the primary efficacy endpoint analysis is defined as the mean change in total sBA concentration from baseline to Week 3.

#### Primary Estimand for Primary Efficacy Endpoint

The primary estimand efficacy endpoint is to evaluate the superior efficacy of volixibat versus placebo for the reduction of elevated sBA concentrations in participants with ICP. The primary comparison of interest is the mean change in sBA concentration comparing baseline with Week 3. The primary comparison will be made regardless of adherence to randomized treatment, treatment modification, or treatment termination and irrespective of any changes in or initiations of allowed concomitant therapies, while assuming that prohibited medications are not available.

The corresponding primary estimand is described by the following 5 attributes:

- Treatments: The randomized treatment administered BID until delivery (with at least 1 dose), regardless of adherence to randomized treatment, treatment modification, or treatment termination
- Population: Participants with ICP who have an sBA concentration  $\geq 20$   $\mu\text{mol/L}$  and an average daily score of  $\geq 4$  on the Adult ItchRO during the screening period. Further population criteria details are provided in [Sections 5.1](#) and [5.2](#).
- Endpoint: Change in the sBA concentration comparing baseline with Week 3
- Population-level summary: Difference in the mean change in the sBA concentration
- Intercurrent events:
  - Change in or administration of any allowed concomitant medication will be handled using a treatment policy strategy.
  - Administration of any prohibited concomitant medication will be handled using a hypothetical strategy assuming that the prohibited medications are not available and hence were not taken, so as to assess the treatment effect for the randomized treatment groups on top of allowed concomitant medication.
  - Discontinuation of randomized treatment due to all of the following reasons will be handled using a treatment policy strategy:
    - Lack of efficacy
    - Safety concerns
    - Lack of compliance to study treatment
  - Delivery prior to 3 weeks of treatment will be handled using a hypothetical strategy, assuming that delivery has not occurred. Few early deliveries are expected prior to Week 3. Participants with sBA  $< 100$  are not likely to give birth prior to 39 weeks, which is at least 3 weeks after the first dose date based on

eligibility criteria (see [Section 8.1.12](#)). Participants with sBA >100 at 34 weeks would have been randomized at least a week earlier (i.e., 33 weeks) because a planned birth within 7 days of randomization is exclusionary. It is anticipated that these participants would still be able to remain on treatment for 3 weeks before giving birth.

- Perinatal death prior to 3 weeks of treatment will be handled using a hypothetical strategy, assuming perinatal death has not occurred. Very few, if any, perinatal deaths are expected prior to Week 3.
- Discontinuation of randomized treatment due to other reasons (including loss to follow-up) will be handled using a hypothetical strategy, assuming that randomized treatment had not been discontinued.
- Liver transplant or death: Neither of these are expected in the study. In the unlikely event of this happening, they will be treated using a composite strategy, assuming worse case for all subsequent assessments.

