## 1. PROTOCOL SUMMARY

### 1.1. Synopsis

Name of Sponsor/Company: Mirum Pharmaceuticals, Inc.	
Name of Investigational Product: Volixibat	
Name of Active Ingredient: Volixibat potassium (formerly SHP626 and LUM002)	
Protocol Number: VLX-401	
Title of Study: A Phase 2a/2b Randomized Double-Blind Placebo-Controlled Study to Evaluate the Efficacy and Safety of Volixibat in Adult Women with Intrahepatic Cholestasis of Pregnancy and Elevated Serum Bile Acid Concentrations (OHANA)	
Study Centers: This study will be conducted at multiple sites across Australia, New Zealand, North America, and the United Kingdom. Other regions may be added.	
Participants: Up to 280 participants will be enrolled in this study. 

Part 1 (open label): Up to 80 participants with serum bile acid (sBA) <math>\geq 10</math> <math>\mu\text{mol/L}</math> during the screening period or at any time during the current pregnancy will be enrolled.

Part 2 (double blind): Approximately 200 participants with a screening sBA level <math>\geq 20</math> <math>\mu\text{mol/L}</math> will be enrolled (100 per arm).

	
Randomization: Part 1 (open label): 

1:1 (volixibat 20 mg twice daily [BID]/volixibat 80 mg BID)

 Part 2 (double blind): 

1:1 (selected volixibat dose BID/placebo BID)

 Randomization will be stratified according to background use of ursodeoxycholic acid (UDCA) or not (in Part 1), gestational age at randomization, presence/absence of gestational diabetes, and highest sBA levels before randomization (in Part 2).	
Study Period: 2020 to 2024	Study Phase: 2a/2b

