### 1.3. Schedule of Activities

**Table 1 Schedule of Activities**

Visit Name	Screening	Treatment Period				Follow-Up		Notes
		Baseline	Weeks 1, 2, 3, etc.	Early Termination*	EOT/Delivery	F1	F2 (EOS)	
Day/Week (Window)	Day -10 to -1	0*	Every 7 Days (±1 Day) Until Delivery		Day of Delivery (+2 Days)	Phone Call: 14 Days after Delivery (±3 Days)	Clinic Visit: 28 Days after Delivery (±3 Days)	
*Participants who early terminate from study drug should still continue with weekly visits through delivery, F1, and F2.
 
Some visits may be conducted as a home health or remote visit at the discretion of the investigator upon approval by the sponsor or designee and in accordance with local and regional regulations.
 
*See Section 8.1.8 for further details on timing of baseline visit.

Administrative Procedures								
Informed consent	X							
Eligibility Procedures								
Inclusion/exclusion criteria	X	X						
Demography	X							
Prior/concomitant treatment	X	X	X	X	X	X	X	
Medical history	X	X						Includes menstrual and obstetric history
Estimated gestational age assessment	X							Confirmation of eligibility based upon estimated gestational age required before randomization: CRL from early ultrasound or head circumference on ultrasound if CRL is >84 mm.

Visit Name	Screening	Treatment Period				Follow-Up		Notes
		Baseline	Weeks 1, 2, 3, etc.	Early Termination*	EOT/Delivery	F1	F2 (EOS)	
Day/Week (Window)	Day -10 to -1	0*	Every 7 Days (±1 Day) Until Delivery		Day of Delivery (+2 Days)	Phone Call: 14 Days after Delivery (±3 Days)	Clinic Visit: 28 Days after Delivery (±3 Days)	*Participants who early terminate from study drug should still continue with weekly visits through delivery, F1, and F2.  Some visits may be conducted as a home health or remote visit at the discretion of the investigator upon approval by the sponsor or designee and in accordance with local and regional regulations. *See Section 8.1.8 for further details on timing of baseline visit.
Hepatitis and HIV screen, TSH	X							If HIV results are documented as negative from the current pregnancy in a participant deemed to be low risk by the investigator, HIV at screening visit may be waived.
Dosing Procedures								
Randomization		X						
Study drug dispensing		X	X					As needed
Study drug collection/reconciliation			X	X	X			As needed
Efficacy Procedures								

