#### **10.4.1.3. Secondary Efficacy Endpoints**

The secondary efficacy endpoints (see [Section 3.2](#)) are designed to evaluate the efficacy of volixibat versus placebo for the treatment of pruritus in participants with ICP as well as composite perinatal outcomes.

The secondary efficacy endpoint for pruritus is defined as the mean change from baseline to Week 3 in the weekly average worst daily itch score as measured by the Adult ItchRO. The worst daily itch score is averaged over the 7 days preceding baseline and over the 7 days preceding each week through Week 3. If >3 days of assessments are missing from a given week, then that weekly average will be set to missing. The analysis of the Adult ItchRO will use an MMRM with a comparable model to that for the primary endpoint. The primary comparison will be made regardless of adherence to randomized treatment, treatment modification, or treatment termination and irrespective of any changes in, or initiations of, allowed concomitant therapies, while assuming prohibited medications are not available and that delivery or perinatal death prior to 3 weeks does not occur.

The attributes for this estimand are the same as for the primary estimand except for the below:

- Endpoint: Change from baseline to Week 3 of the study treatment period in the weekly averaged worst daily itch score as measured by the Adult ItchRO (average of the 7 days preceding baseline and of the 7 days preceding Week 3).
- Population-level summary: Difference in the mean change in the weekly averaged worst daily itch score

The secondary efficacy endpoint for composite perinatal outcomes is defined as the proportion of participants that experience any of the 4 outcomes specified in [Section 3.2](#). The comparison of interest is the proportion of participants meeting the composite outcome. The primary comparison will be made regardless of adherence to randomized treatment, treatment modification, or treatment termination and irrespective of any changes in, or initiations of, allowed concomitant therapies, while assuming prohibited medications are not available.

The attributes for this estimand are the same as for the primary estimand except for the below:

- Treatments: The randomized treatment administered BID until day of delivery (with at least 1 dose), regardless of adherence to randomized treatment, treatment modification, or treatment termination.

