#### **6.1.2. Estimand and Analysis of the Treatment Effect**

The estimand for the treatment effect will be the mean difference between volixibat and placebo for the change from baseline in sBA at Week 3.

The primary analysis will be conducted in the primary cohort using the modified ITT (mITT) population. A restricted maximum likelihood (REML)–based mixed-effects model for repeated measures (MMRM) will be used including weekly postbaseline change from baseline in total sBA during the core study period (double-blind treatment period) through Week 3, as the dependent variable and the fixed, continuous effects of baseline sBA and gestational age, fixed categorical effects of presence/absence of gestational diabetes, treatment group, visit, and treatment group by-visit interaction as covariates and participant as a random effect.

The unstructured variance/covariance matrix will be used to model the variances and covariances for the time points included in the model. The unstructured variance/covariance does not impose any restrictions on the pattern of the matrix elements. The use of an endpoint 3 weeks after baseline should result in minimal amounts of missing data. Every attempt (e.g., relaxing the convergence criteria, increasing the iteration limit, choosing reasonable starting values for the estimates) will be made to ensure convergence using the unstructured modeling of within-participant correlations. However, if the numerical algorithm for estimation of the mixed model fails to converge, the following variance/covariance matrix structures will be used in the following order: 1) heterogeneous Toeplitz, 2) heterogeneous compound symmetry, and 3) heterogeneous autoregressive of order 1. The first (co)variance structure that does not have a convergence problem will be the one used for the analysis. The Kenward-Roger approximation (1997) will be used to estimate denominator degrees of freedom.

The primary efficacy analysis will compare volixibat and placebo using the contrast (difference in least squares [LS] means) between treatment groups at Week 3. Significance tests will be based on LS means using a 2-sided significance level (2-sided 95% CIs).

The null hypothesis for the primary efficacy endpoint of the equality of volixibat and placebo is:

H0: mean change in total sBA baseline and Week 3 in the two treatment groups are equal

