### 6.1.3. Intercurrent Events and Handling Strategies

The following table listed outs some potential intercurrent events that may impact the estimation of the primary estimand of the study. For each type intercurrent event, we proposed handling strategies:

Events	Potential Consequences	Handling Strategy
Early discontinuation and/or missing because of:  1. Lack of efficacy; physician decision; or required prohibited medication;  2. Adverse events or death;  3. Noncompliance to study drug;  4. Other reasons for treatment discontinuations	
 
• Confounded treatment effect
 
	Hypothetical Policy 
 
• Sensitivity Analysis:               
 
– MAR
 
– MNAR
 
 
 

Concomitant Medications	
 
• More difficult to pinpoint           
 
○ Administered as needed for both active treatment and placebo
 
○ May lead to various impacts on participants' treatment/safety/efficacy
 
 
 
	Randomization/Treatment Policy
Other Intrinsic/extrinsic factors 
 
• Stratification factors
 
• Age
 
• Sex
 
• Race/Ethnicity
 
	
 
• Differentiated treatment effects
 
	Principal Stratum Policy 
 
• Stratified analyses
 
• Subgroup analyses
 
• Covariate adjusted analyses
 

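### Three confirmatory estimands assume prohibited medication was not taken, but no confirmatory analysis sets aside or models data observed after a prohibited drug

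*Protocol*

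**What the plan says.** **Estimands.** Protocol 10.4.1.1 puts allowed concomitant medication under treatment policy and treats prohibited medication differently: "Administration of any prohibited concomitant medication will be handled using a hypothetical strategy assuming that the prohibited medications are not available". Protocol 10.4.1.3 describes the ItchRO and composite comparisons in the same terms: "irrespective of any changes in, or initiations of, allowed concomitant therapies, while assuming prohibited medications are not available". These are the three endpoints in the testing hierarchy (Protocol 10.4.1.2, SAP 3.5).

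**Analyses.** The primary test is an MMRM in the mITT population, described in SAP 6.1.2 as "including weekly postbaseline change from baseline in total sBA during the core study period (double-blind treatment period) through Week 3". ItchRO uses a comparable MMRM, and the composite uses a stratified CMH test. None of these descriptions mentions data collected after a prohibited drug.

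**SAP intercurrent events.** SAP 6.1.3 has one row for concomitant medications, handled by "Randomization/Treatment Policy", with no split between allowed and prohibited. A different row, on early discontinuation and missing data, lists the need for a prohibited medication among its reasons and labels the strategy hypothetical.

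**Follow-up.** Stopping study drug does not stop data collection. Protocol Table 1 says: "Participants who early terminate from study drug should still continue with weekly visits through delivery, F1, and F2".

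**The concern.** An MMRM under missing at random predicts what is missing; it does not alter what was observed. If a participant takes a prohibited drug and her sBA or itch score is still recorded, that value enters the model as it stands. The result is a treatment-policy estimate of an effect that the protocol defines as if the drug had not been taken. The CMH test likewise counts the perinatal outcome that occurred.

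The drugs matter to the endpoints. Protocol 6.8.2 prohibits rifampin, bile acid resins, S-adenosylmethionine, UDCA outside the permitted uses, and antipruritic changes outside the rescue rule. Protocol 2.2.1 reports lower sBA with rifampicin plus UDCA, and some maternal benefit with cholestyramine and S-adenosylmethionine.

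At stake is whether the confirmatory results can be reported under the estimands stated for them, and whether the handling of such values is fixed in advance or left to a choice made after the data are seen.

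**Working it through.** **1. Does any analysis carry out the hypothetical strategy?**

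- Primary MMRM (Protocol 10.4.1.1, SAP 6.1.2): weekly values through Week 3, no exclusion rule.
- ItchRO MMRM (Protocol 10.4.1.3, SAP 6.2): a comparable model, no exclusion rule.
- Composite CMH (same sections): no rule for prohibited medication.
- De jure analysis (Protocol 10.4.1.1, SAP 6.1.5): drops data after rescue medication. Rescue is permitted under Protocol 6.8.1.2, and this analysis is supportive.
- SAP 6.1.7, missing category 1: covers participants who stopped treatment because a prohibited medication was required and whose sBA is missing. It is a sensitivity imputation and does not touch observed values.

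None of these removes or models values observed after a prohibited drug in a confirmatory test.

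**2. The plan's own figure.** Protocol 10.1 states that "a sample size of 100 participants per arm has 80% power to detect mean difference of 10 with standard deviation of 25", with two-sided alpha 0.05 and 1:1 allocation.

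- SE = 25 × √(1/100 + 1/100) = 3.536.
- Power = Φ(10/3.536 − 1.96) = Φ(0.868) = 80.7%; the noncentral t with 198 df gives 80.4%.
- The required size is 99 per arm. The stated figure reproduces, so the sample size is not in dispute.

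**3. What the mismatch could do.** The documents give neither a rate of prohibited use nor an effect on sBA, so both are assumptions. Let e be the proportion using the drug in one arm, with none in the other, and g the reduction in sBA among users. The difference under the stated estimand is taken as 10.

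- Use on placebo: as-observed target = 10 − e × g; power = Φ(target/3.536 − 1.96). If the users' values are set to missing instead, the target stays at 10 and SE = 25 × √(1/100 + 1/[100(1 − e)]).
- Use on volixibat: as-observed target = 10 + e × g. If the difference under the stated estimand is zero, the rejection rate is 1 − Φ(1.96 − eg/3.536) + Φ(−1.96 − eg/3.536).

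| e | g (µmol/L) | Placebo use: target | Power as observed | Power if set to missing | Volixibat use: target | Rejection if stated difference is 0 |
|---|---|---|---|---|---|---|
| 5% | 5 | 9.75 | 78.7% | 79.7% | 10.25 | 5.1% |
| 10% | 10 | 9.0 | 72.1% | 78.6% | 11.0 | 5.9% |
| 10% | 20 | 8.0 | 61.9% | 78.6% | 12.0 | 8.7% |
| 20% | 20 | 6.0 | 39.6% | 76.0% | 14.0 | 20.5% |

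With e = 0 the two targets coincide.

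**4. Price of the repair.** If 5%, 10%, 15% or 20% of each arm lost Week 3 this way, power would be 78.7%, 76.5%, 74.1% or 71.6%, with no credit for information from earlier visits.

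**The case against.** **The SAP does recognise prohibited medication.** A reader might infer that the SAP places all concomitant medication under treatment policy. It does not. SAP 6.1.3 treats a required prohibited medication as hypothetical when it leads to discontinuation or missing data, and SAP 6.1.7 uses that reason in an imputation. This stands, and it narrows the point to prohibited use with data still collected.

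**The SAP is out of step.** SAP Section 1 says it is based on protocol Version 1, so part of the conflict between the documents may be stale text. This also stands, but the current protocol has the same gap between its estimands and its own analysis sections.

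**Use may be rare.** Participants must agree to refrain from several of these drugs (inclusion criterion 5), and Protocol 6.8.1.2 allows UDCA and antipruritics as rescue, which leaves them under treatment policy by design. Low use is plausible, though no rate is given.

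**Direction and size are not established.** A reader might infer that the retained values pull the effect towards zero and cut power to about 40%. The documents support neither. Which arm would use more is not stated, and Protocol 6.8.2 also prohibits cholestasis-inducing drugs, which could plausibly raise sBA. The 40% figure needs an extreme pair of assumptions.

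**Treatment policy throughout would also be consistent.** True, but it would change the question for sBA and ItchRO, where the protocol deliberately separates allowed from prohibited drugs.

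**Conclusion.** The point holds as a mismatch between estimand and analysis. Prohibited use with data still collected is analysed as treatment policy in all three confirmatory tests, while the protocol defines the effects as if those drugs had not been taken. The undivided SAP row contradicts Protocol 10.4.1.1, so this is more than missing detail.

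The numerical consequence is unknown. Negligible use before Week 3 (before the perinatal outcome is known, for the composite) makes no difference. Excess use of an sBA-lowering drug on placebo attenuates the sBA effect, and excess use on volixibat inflates it. The tabulated shifts of 0.25 to 4.0 µmol/L against a planned 10 rest entirely on assumed rates and effects and are not forecasts. The change should be made because it is cheap and has to be fixed before unblinding.

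**What to change.** Before unblinding:

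1. In Protocol 10.4.1.1 and 10.4.1.3 and SAP 6.1.2 and 6.2, state that sBA and ItchRO values after the first Section 6.8.2 prohibited medication are set to missing in the confirmatory MMRMs. Apply this to any prohibited drug, as the estimand says, or narrow the estimand to a prespecified list of drugs acting on the endpoint. State that the rule takes precedence when the participant has also stopped study drug; otherwise someone who stops for lack of efficacy and then starts rifampin falls under two strategies. Add missing-not-at-random sensitivity analyses and keep the all-data fit as supportive.
2. Split the concomitant-medication row in SAP 6.1.3 into allowed (treatment policy) and prohibited (hypothetical).
3. For the composite, replace the assumption that prohibited drugs are unavailable with treatment policy, which is what the CMH test estimates. Deleting data cannot recover the outcome that would have occurred without the drug.

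The cost is wording plus one derived flag from medication dates that Protocol 6.8 already requires. Some observed Week 3 values become missing, with a small loss of precision if use is low.
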